5.2 Dose Modification/Study Discontinuation

Toxicity: NCI common toxicity version 4 will be utilized to assess toxicity.

Every effort should be made to administer the full dosing regimen of Radium Ra 223 dichloride. Adjustment of dose level is not permitted.

- Blood transfusion at baseline is acceptable to obtain baseline value of ≥ 9 and between study drug administrations, but not on the same day as Xofigo administration. Use of biologic myeloid growth factors such as G-CSF, is allowed in the management of acute toxicity.

Gastrointestinal events:

Diarrhea should be treated as per local institutional practices. The next cycle should not begin before diarrhea is recovered to CTCAE v4 Grade 2 or less.

Nausea or vomiting should be treated as per local practice. A further dose of study medication should not be given before nausea or vomiting is recovered to CTCAE v.4 Grade 2 or baseline levels.

Xofigo will be permanently discontinued for the following:

- Symptomatic Skeletal Event:
 - Pathologic fracture: Pathologic fractures are to be treated in a manner that attempts to maintain the best functional status and quality of life. Study treatment should be discontinued if the pathologic fractures are due to disease.
 - Spinal cord compression: If the patient experiences spinal cord compression during the treatment period, the patient should be treated for the event, and may not receive further study drug administration.
 - Radiation therapy to bone
 - Surgery to bone
- Patients with lung cancer progression requiring treatment with chemotherapy, radiation or surgery.
- Unacceptable toxicity (see section 5)
- **Surgical Intervention:** If surgery is required, and not due to disease progression, the patient may continue with study treatment, following a period of at least 4 weeks, if this is considered safe in the treating Investigator's opinion.
- **Non-pathological fractures:** For traumatic fractures in weight-bearing bones during treatment phase, the study drug administration should be discontinued.
- Incidental, asymptomatic new or worsening bone metastases will not require discontinuation of Xofigo.

6.0 SCHEDULE OF EVALUATIONS / STUDY CALENDAR

Parameter	Pre-study (to be sent to BrUOG prior to registration)	Prior to each Day 1 of Each Cycle (within 7 days) (Every 4 weeks) ^{CK}	At study completion for all patients(30 days- 5 weeks post last dose of Xofigo)	FU ^H
Informed Consent (within 30 days of day 1) *pts are to be re-consented if ICF will be outside 30 day window	X			
History , Demographics (baseline only)	X			
Physical examination	X	X	X	
Weight	X	X ^K	X	
Vital signs	X	X ^K	X	
Toxicity Assessment	X	X ^E	X ^{EF}	
QOL questionnaires ^A	X	X	X	
Performance Status	X	X	X	
CBC, diff, platelet count ^C	X (within 14 days)	X	X	
Alk phos ^C	X (within 14 days)	X	X	
T. bili, AST, ALT, Cr, albumin ^C	X (within 14 days)			
Serum Pregnancy ^{B,C}	X (within 7 days of drug)			
CT scan of Chest/abd/pelvis ^{DG}	X ^D (within 28 days)	Per treating physician	Per treating physician	Per treating physician
Bone Scan	X ^J			
Brain imaging (CT or MRI)- contrast to be used unless documented allergy or inadequate renal function	X ^I			
Survival and Disease status			X	X ^H

^A See Appendix F for EORTC QLQ-C30 and QOL-BM22 questionnaires. Quality of life to be at baseline, after completion of cycles 2, 4, and 6, and end of treatment. If patients complete 6 cycles, end of cycle 6 questionnaire to count for end of treatment questionnaire as well.

^B Post-menopausal women (surgical menopause or lack of menses \geq 12 months) do not need to have a pregnancy test, document status.

^C It is appropriate to use labs from screening for cycle 1 day 1, if labs are within 14 days (pregnancy must be within 7 days as noted above for applicable patients). It is required that if labs are re-drawn prior to day 1 cycle 1 that ANC must be \geq 1.5, PLT \geq 100k, HGB \geq 9 prior to cycle 1 dosing or dosing must be delayed

until criteria are met. It is appropriate to use physical, weight, vitals, toxicity assessment and PS from screening for cycle 1 day 1 if within 14 day screening window.

^D CT Scan for disease assessment should be performed within 28 days of study entry. A PET scan may substitute for a CT scan. Report required.

^E All patients removed from the study for any reason, including completion will have toxicity assessments performed at time of removal from study.

^F Adverse event evaluation, inclusive of SAE evaluation, and Performance status assessment will be done 30 days (+1 week) post last dose of drug. SAEs occurring outside this 30 day window must be reported if the event is considered to be possibly related to the drug. If a patient begins a new treatment, AE evaluation will be stopped unless the patient experiences an event that is thought to be possibly related to the study treatment. SAEs will continue to be captured even if patient begins a new treatment within the 30 day window if event thought to be possibly related to Xofigo..

^G Although it is not a study requirement, it is suggested that CT scans be completed approximately every 2 months (approximately every 2 cycles) or per treating physician.

^H The time to first progression and the time to first SSE is to be reported to BrUOG on a 2-3 month basis. Overall survival is to be reported every 2-3 months. Follow-up will be for 1 year.

^I For patients with treated brain metastases must have brain imaging showing evidence of stability prior to first dose of Xofigo. Scan must be sent to BrUOG with registration information before patient is registered on study.

^J: A bone scan is required to have been done or to be done on each patient prior to registration. Bone scan results required to be sent to BrUOG for registration. However, the bone scan is not required to be positive as long as other imaging or pathology/cytology is positive for bone metastases. Documentation to be sent to BrUOG.

^K: It is required that weight and vitals be captured the day of infusion, prior to drug administration and these values be reported to BrUOG even if patient already had weight and vitals done pre-cycle within 7 day window. If patient has weight done 7 days before dosing and then again pre-drug administration (day of), unless patient's weight changed by > 10% (since the +7 day assessment) then drug can be administered. Pre-cycle weight to be used for drug ordering and drug dosing. Day of weight is only to be used to confirm % of weight change if applicable.

**Any radiographic scans or tests, such as MRIs, PETs, CTs, Bone Scans (etc) that are performed before, during or after study treatment (up to 1 year) , to be submitted to BrUOG

6.1 Patient Assessments:

Patients will undergo a baseline radiographic assessment with either a CT scan or PET scan after completion of 1st-line treatment as per institutional standard of care. Patients meeting study eligibility may be entered on the study. Patients will have a physical monthly prior to each Xofigo treatment. Patients with new signs or symptoms suggesting bone metastases, or other sites of disease progression, will have additional radiographic assessment for evaluation as per institutional standards. The primary endpoint will be the assessment of how many patients develop an SSE during the study treatment and in particular during the first 4 cycles (approximately 4 months) on study. Following completion of all 6 treatments, patients will undergo restaging radiographic studies as per institutional standard of care.

6.2 Alkaline Phosphatase Assessment:

Alkaline phosphatase was found to be an important biomarker in the ALSYMPCA trial.¹⁶ Alkaline phosphatase levels will be assessed at study entry and prior to each dose of Xofigo. We will secondarily assess the following: 1. Time to an increase in alkaline phosphatase by $\geq 25\%$ from baseline, 2. Alkaline phosphatase response (reduction of $\geq 30\%$ from baseline value), and 3. Normalization of the alkaline phosphatase level (defined as a return to normal range in patients with an elevated level at baseline).

6.3 Quality of Life Assessments:

The EORTC QLQ-C30 and BM22 questionnaires will be performed monthly prior to each administration of Xofigo, and at study completion. The EORTC QLQ-30 assesses quality of life in patients with cancer, and the BM22 assesses quality of life in patients with bone metastases.¹⁷

7.0 DEFINITION OF PROGRESSION:

Progression

- 7.1 Progression of bone metastases Symptomatic Skeletal Event:
 - Pathologic fracture: Pathologic fractures are to be treated in a manner that attempts to maintain the best functional status and quality of life. Study treatment should be discontinued if the pathologic fractures are due to disease.
 - Spinal cord compression: If the patient experiences spinal cord compression during the treatment period, the patient should be treated for the event, and may not receive further study drug administration.
 - Radiation therapy to bone
 - Surgery to bone
- Incidental, asymptomatic new or worsening bone metastases will not require discontinuation of Xofigo.

7.2 Progression of lung cancer will be evaluated in this study using the international criteria proposed in the Revised Response Evaluation Criteria in Solid Tumors (RECIST) Guideline version 1.1

Measurable disease: Measurable lesions are defined as those that can be accurately measured in at least one dimension (longest diameter to be recorded) as ≥ 20 mm by chest x-ray, as ≥ 10 mm with CT scan, or ≥ 10 mm with calipers by clinical exam. All tumor measurements must be recorded in millimeters (or decimal fractions of centimeters).

Non-measurable disease: All other lesions (or sites of disease), including small lesions (longest diameter <10 mm or pathological lymph nodes with ≥ 10 to <15 mm short axis).

- Patients with lung cancer progression requiring treatment with chemotherapy, radiation or surgery will be removed from the study. Patients not requiring treatment with chemotherapy, radiation, or surgery may continue on study at physician discretion.

Progressive Disease (PD):	At least a 20% increase in the sum of diameters of target lesions, taking as reference the smallest sum on study (this includes the baseline sum if that is the smallest on study). In addition to the relative increase of 20%, the sum must also demonstrate an absolute increase of at least 5 mm. (Note: the appearance of one or more new lesions is also considered progressions).
---------------------------	--

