3.1.9 Concurrent treatment with bisphosphonates and denosumab is allowed. Information on start and stop date and drug with dose to be sent to BrUOG if patient to be treated concurrently.

3.1.10 Prior skeletal related events (pathologic fracture, radiation or surgery to bone, or spinal cord compression) are allowed if they have been managed and now patient is stable for 4 weeks prior to study entry. Must submit how events managed to BrUOG for documentation to confirm eligibility criterion. (For example, if a patient experienced a SSE and had radiation for 2 weeks they must then be stable for 4 weeks after the completion of radiation prior to study entry)

3.1.11 Subjects must be able to understand and be willing to sign the written informed consent form.

3.1.12 All acute toxic effects related to prior treatment(s) must have resolved to NCI-CTCAE v4 Grade 1 or less at the time of registration except for alopecia. Please note blood transfusion is allowed at baseline to bring HGB within study requirements, see section 5.2

3.1.13 Women of childbearing potential must have a negative serum pregnancy test performed within 7 days prior to the start of study drug. Post-menopausal women (defined as no menses for at least 1 year) and surgically sterilized women are not required to undergo a pregnancy test.

3.1.14 Subjects (men and women) of childbearing potential must agree to use adequate contraception beginning at the signing of the ICF until at least 30 days after the last dose of study drug. The definition of adequate contraception will be based on the judgment of the treating physician.

[figure not shown]
3.1.15 Willing and able to comply with the protocol, including follow-up visits and examinations

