3.2 Conditions for Patient Ineligibility

- 3.2.1 Received systemic therapy with radionuclides (e.g., strontium-89, samarium-153, rhenium-186, or rhenium-188, or Radium Ra 223 dichloride) for the treatment of bony metastases
- 3.2.2 No prior invasive malignancy within the prior two years. However, patients with an early stage malignancy that is not expected to require treatment in the next 2 years (such as early stage, resected breast cancer or asymptomatic prostate cancer) are eligible
- 3.2.3 Untreated brain metastases.
- 3.2.4 Any other serious illness or medical condition that in the investigator's opinion would interfere with protocol treatment, such as but not limited to: Any active infection \geq National Cancer Institute Common Terminology Criteria for Adverse Events (NCI-CTCAE) version 4 Grade 2 or Cardiac failure New York Heart Association (NYHA) III or IV
- 3.2.5 Women who are pregnant or breast-feeding.
- 3.2.6 Inability to comply with the protocol and/or not willing or who will not be available for follow-up assessments.
- 3.2.7 Any condition which, in the investigator's opinion, makes the subject unsuitable for trial participation.
- 3.2.8 Concurrent anti-cancer therapy (chemotherapy, radiation therapy, surgery, immunotherapy, biologic therapy, or tumor embolization) other than Ra 223 dichloride.
- 3.2.9 Major surgery within 28 days of starting study drug. Central venous catheter placement is not considered major surgery.

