5.0 TOXICITIES, DOSE MODIFICATIONS, AND MANAGEMENT

5.1

If labs are re-drawn post enrollment and prior to cycle 1 day 1 dosing, the following criteria are required to be met before dosing cycle 1:

- ANC must be ≥ 1.5 prior to day 1 dose of treatment (cycle 1)
- (PLT) count must be $\geq 100,000/\text{mm}^3$ prior to day 1 dose of treatment (cycle 1)
- Hemoglobin (Hgb) must be $\geq 9\text{g/dl}$ prior to day 1 dose of treatment (cycle 1)

A new course (cycle 2-6) of treatment should not begin until the following criteria are met:

- Platelets $\geq 50,000 \times 10^9/\text{L}$
- Granulocytes $\geq 1000 \times 10^9/\text{L}$ ($1000/\text{mm}^3$)
- Recovery from other treatment related, non-hematologic toxicities to \leq Grade 2
- Diarrhea \leq grade 2
- Nausea or vomiting \leq grade 2 or to baseline levels

If the patient does not meet these criteria delay day 1 until these requirements are met. Patients who require a treatment delay of more than 4 weeks from the scheduled treatment day due to toxicity will be removed from protocol treatment.

Weight prior to cycles 2-6 can be taken up to 7 days prior to dosing each cycle. Weight within 7 days of each cycle to be used for drug order and drug dosing for that cycle. Weight must again be assessed the day of drug administration, but this weight is only to be used to confirm patient's weight has not changed by $> 10\%$ since the prior assessment pre-dosing (for example 7 days prior). If weight has not changed by $> 10\%$ then, the patient is considered okay to treat. See section 6 subscript K for more details

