Dehydration occurred in 3% of patients on Radium Ra 223 dichloride and 1% of patients on placebo. Radium Ra 223 dichloride increases adverse reactions such as diarrhea, nausea, and vomiting which may result in dehydration. Monitor patients' oral intake and fluid status carefully and promptly treat patients who display signs or symptoms of dehydration or hypovolemia.

Injection Site Reactions

Erythema, pain, and edema at the injection site were reported in 1% of patients on Radium Ra 223 dichloride.

Secondary malignant neoplasms

No cases of radiation-induced cancer have been reported in reported in clinical trials with radium-223 dichloride in follow-up of up to three years. However, the radiation dose resulting from therapeutic exposure may result in higher incidence of cancer (e.g. sarcomas of the bone, or leukemia), mutations and a potential for development of hereditary defects.

Hematologic	Xofigo (n=600)		Placebo (n=301)	
	Grades 1-4	Grades 3-4	Grades 1-4	Grades 3-4
Laboratory	%	%	%	%
Anemia	93	6	88	6
Lymphocytopenia	72	20	53	7
Leukopenia	35	3	10	<1
Thrombocytopenia	31	3	22	<1
Neutropenia	18	2	5	<1

Bone Marrow Suppression

In the randomized trial, 2% of patients on the Radium Ra 223 dichloride arm experienced bone marrow failure or ongoing pancytopenia compared to no patients treated with placebo. There were two deaths due to bone marrow failure and for 7 of 13 patients treated with Radium Ra 223 dichloride, bone marrow failure was ongoing at the time of death. Among the 13 patients who experienced bone marrow failure, 54% required blood transfusions. Four percent (4%) of patients on the Radium Ra 223 dichloride arm and 2% on the placebo arm permanently discontinued therapy due to bone marrow suppression.

In the randomized trial, deaths related to vascular hemorrhage in association with myelosuppression were observed in 1% of Radium Ra 223 dichloride-treated patients compared to 0.3% of patients treated with placebo. The incidence of infection-related deaths (2%), serious infections (10%), and febrile neutropenia (<1%) were similar for patients treated with Radium Ra 223 dichloride and placebo.

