11.3.1 Pregnancies

Pregnancies occurring while the subject is on study drug or within 4 weeks after the subject's last dose of study drug are considered expedited reportable events. If the subject is on study drug, the study drug is to be discontinued immediately. The pregnancy must be reported to the Brown University Oncology Research Group with 24 hours and BrUOG will in turn report to Bayer within 24 hours (1 working day) of the Investigator's knowledge of the pregnancy by email and/or facsimile using the SAE Form. Pregnancies and suspected pregnancies (including a positive pregnancy test regardless of age or disease state) of a female subject occurring while the subject is on IP, or within 4 weeks (30 days) of the subject's last dose of IP, are considered immediately reportable events. IP is to be discontinued immediately. The pregnancy, suspected pregnancy, or positive pregnancy test must be reported to Bayer Drug Safety immediately by facsimile, or other appropriate method (to be done by BrUOG), using the Medwatch3500A form (MedWatch 3500A-to be completed by site).

The Investigator will follow the subject until completion of the pregnancy, and must notify Bayer (by informing BrUOG) of the outcome as specified below. The Investigator will provide this information as a follow-up to the initial report. If the outcome of the pregnancy meets the criteria for immediate classification as a SAE (i.e., spontaneous abortion [any congenital anomaly detected in an aborted fetus is to be documented], stillbirth, neonatal death, or congenital anomaly), the Investigator should follow the procedures for reporting SAEs (i.e., report the event to BrUOG who will then report to Bayer by facsimile within 24 hours (1 working day) of being made aware of the event).

Any suspected fetal exposure to Xofigo ® must be reported to BrUOG within 24 hours who will then report to Bayer within 1 working day of being made aware of the event. The patient should be referred to an obstetrician/gynecologist experienced in reproductive toxicity for further evaluation and counseling.

All neonatal deaths that occur within 30 days of birth should be reported, without regard to causality, as SAEs. In addition, any infant death after 30 days that the Investigator suspects to be related to the in utero exposure to the study drug should also be reported. In the case of a live "normal" birth, Bayer should be advised as soon as the information is available.

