12.0 REMOVAL OF PATIENTS FROM PROTOCOL THERAPY

Extraordinary medical circumstances or withdrawal of consent by the patient: If, at any time, the constraints of this protocol are detrimental to the patient's health, and/or the patient no longer wishes to continue protocol therapy, the patient shall be withdrawn from protocol therapy. Patients will also be withdrawn from study for the following reasons:

1. **Disease Progression: Any patient with disease progression should be removed from study as per section 7.1 and 7.2. Details and tumor measurements should be documented on flow sheets.**
2. Patient is unable to tolerate the toxicity resulting from the study treatment, even with optimal supportive care, in the opinion of the Treating Physician. Adverse event(s) that, in the judgment of the investigator, may cause severe or permanent harm or which rule out continuation of study drug.
3. The physician feels it is in the best interest of the patient to stop the treatment.
4. Inter current illness that would, in the judgment of the Investigator, affect assessment of clinical status to a significant degree or require discontinuation of study treatment

5. Non protocol chemotherapy or immunotherapy is administered during the study
6. Noncompliance with protocol or treatment—major violation
7. Pregnancies or Suspected Pregnancies(including positive pregnancy test)
8. Patient is lost to follow-up
9. Patient refuses to continue treatment (patient will continue to be followed for disease-free survival and overall survival)
10. Death

In this event notify:

Brown University Oncology Research Group (BrUOG) Central Office,
[contact]
[contact]

The BrUOG Central Office will in turn notify the Principal Investigator.

***Document the reason(s) for withdrawal on flow sheets. Follow the patient for survival with follow-up forms as dictated by the protocol**

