APPENDIX B: Checklist

BrUOG L301: Xofigo Following Frontline-Line Chemotherapy For Patients With Non-Small Cell Lung Cancer and Bone Metastases

Inclusion Criteria

(y/n) Advanced non-small cell lung cancer with bone metastases

(y/n) Stable or responding disease after completion of initial systemic chemotherapy as defined by RECIST criteria. Site to submit pre-treatment scan with post treatment scan for RECIST and confirmation to BrUOG. Document blastic or lytic lesions (and for lytic soft tissue or no soft tissue component. Soft tissue component requires measurements for RECIST).

(y/n) At least 3 weeks have elapsed since prior chemotherapy and 4 weeks since radiation prior to first dose of Xofigo. Patients are not permitted to receive any form of 'maintenance' chemotherapy or biologic/targeted anticancer therapy while being treated on this study

(y/n) Voluntary, signed written informed consent, Date signed _____

(y/n) Age ≥ 18

(y/n) Must be willing to consent to use effective contraception while on treatment and for at least 30 days afterwards.

(y/n) CT scan of chest/abdomen prior to registration (PET scan can substitute), report to be submitted to BrUOG

(y/n) Labs within 14 days of study registration: Date: _____

(y/n) serum pregnancy test negative within 7 days of beginning study drug for women of childbearing potential: Date if applicable: if not applicable because patient is male document with N/A. If post-menopausal female (defined as no menses for at least 1 year) then document here with N/A and write in note to submit to BrUOG

(y/n) Subjects (men and women) of childbearing potential must agree to use adequate contraception beginning at the signing of the ICF until at least 30 days after the last dose of study

drug. The definition of adequate contraception will be based on the judgment of the treating physician.

_____ (y/n) Absolute neutrophil count \geq 1,500/ μ l, Date _____

_____ (y/n) WBC \geq 3,000/ μ m³; date: _____

_____ (y/n) Platelet \geq 100,000/ μ L, Date _____

_____ (y/n) HGB \geq 9g/dl: Date: _____

_____ (y/n) Total bilirubin \leq 1.5 x ULN, Date _____

_____ (y/n) AST \leq 2.5x ULN, ALT \leq 2.5x ULN, albumin $>$ 2.5g/dl Institution Date _____

_____ (y/n) creatinine \leq 1.5xULN Date: _____

_____ (y/n) All acute toxic effects related to prior treatment(s) must have recovered to \leq grade 1 except for alopecia at time of registration.

_____ (y/n) ECOG 0-1

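### Low-priority safety improvement: the only scheduled pregnancy test precedes cycle 1, and none is required before radium cycles 2 to 6

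*Protocol*

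**What the plan says.** The Serum Pregnancy row of the calendar (Protocol Section 6.0) contains one entry, "X (within 7 days of drug", in the pre-study column. Its cells for the pre-cycle visit, study completion and follow-up are empty. Footnote C gives the 7-day pregnancy window only while explaining which screening results may serve for cycle 1 day 1. Section 3.1.13 agrees: women of childbearing potential "must have a negative serum pregnancy test performed within 7 days prior to the start of study drug". Appendix B asks for "serum pregnancy test negative within 7 days of beginning study drug for women of childbearing potential", and its exclusion part again places the test before treatment begins.

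For later doses, Section 5.1 states: "A new course (cycle 2-6) of treatment should not begin until the following criteria are met". The list that follows covers platelets, granulocytes, recovery from non-hematologic toxicity, diarrhea, and nausea or vomiting. It has no pregnancy test. Section 5.2 and the pre-dose blood count text in Section 9.1.11 add none.

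The Protocol does act on pregnancy once it is known or suspected. Section 3.2.5 excludes "Women who are pregnant or breast-feeding". Section 11.3.1 says "If the subject is on study drug, the study drug is to be discontinued immediately", makes a positive test immediately reportable, and requires suspected fetal exposure to be reported within 24 hours with referral to an obstetric specialist. Section 12.0 item 7 lists "Pregnancies or Suspected Pregnancies(including positive pregnancy test" among the reasons for withdrawal. The SAP does not touch the point.

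**The concern.** One of the triggers of the stopping rule is a positive pregnancy test, but after cycle 1 no such test is scheduled. Up to five further doses of a radionuclide can be given on the strength of one baseline result. Between doses, protection rests on contraception (3.1.14, with adequacy left to the treating physician), the physical and toxicity assessment before each dose (6.0, 6.1), and clinical suspicion. Suspicion may be slow here: Section 9.1.11 lists nausea in 36% and vomiting in 19% of treated patients, so early symptoms of pregnancy could be put down to the drug.

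What is at stake is fetal exposure from further doses given before a pregnancy is recognized. Section 11.3.1 already treats that exposure as serious enough for urgent reporting and referral.

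**Working it through.** The plan states no figure to reproduce. The check is a reading of the sections set out above, followed by schedule arithmetic and a rough sizing.

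**1. Is the blank cell real?** The calendar row, footnote C, 3.1.13, Appendix B and the 5.1 list all agree, so the blank is not an artefact of the table layout.

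**2. Age of the single test.** Six doses every 4 weeks (4.1) fall on days 0, 28, 56, 84, 112 and 140. The test is done 0 to 7 days before dose 1. At dose k its age is 28(k − 1) to 28(k − 1) + 7 days:
- dose 2: 28 to 35 days
- dose 6: 140 to 147 days

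Permitted delays lengthen this.

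**3. Further doses per pregnancy.** Assumptions, none from the documents: conception is uniform over days 0 to 140; clinical recognition comes 28 to 84 days after conception; a test turns positive 10 to 14 days after conception and is done 0 to 7 days before dosing, so detection takes 10 to 21 days. If all six doses are given, the mean number of doses falling within L days after conception is

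M(L) = (1/140) × Σ min(L, d), over d = 28, 56, 84, 112, 140.

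| L (days) | Sum | M(L) |
|---|---|---|
| 10 | 5 × 10 = 50 | 0.357 |
| 21 | 5 × 21 = 105 | 0.75 |
| 28 | 5 × 28 = 140 | 1.0 |
| 56 | 28 + 4 × 56 = 252 | 1.8 |
| 84 | 28 + 56 + 3 × 84 = 336 | 2.4 |

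Saving per pregnancy: from 1.0 − 0.75 = 0.25 to 2.4 − 0.357 = 2.04 doses.

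**4. Whole trial.** Assume 0 to 3 women of childbearing potential among the 36 patients, each with a 1 to 5% chance of pregnancy. Expected pregnancies are 0 to 3 × 0.05 = 0.15. The largest expected saving is 0.15 × 2.043 = 0.31 doses; the smallest is 0.

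**5. Allowing for stopping at a symptomatic skeletal event (SSE).** Weight each dose on day d by exp(−hd), with h = −ln(1 − p)/112 and p = 20% or 40% by 4 months (the rates in Section 17.0).
- p = 0.2: (1.988 − 0.303) × 0.15 = 0.25 doses
- p = 0.4: (1.572 − 0.247) × 0.15 = 0.20 doses

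**6. The other side of the ledger.** Extra assays: 5 per woman, so 0 to 15. At an assumed false-positive rate of 0.1 to 1% per test, at most 15 × 0.01 = 0.15 false positives are expected. If each ended treatment, one before dose 2, 3, 4, 5 or 6 would cost 5, 4, 3, 2 or 1 doses, which sum to 15. At 1% the expected loss is 3 × 0.01 × 15 = 0.45 treatment doses; at 0.1% it is 0.045. With the SSE weighting, the 1% figure becomes about 0.37 (p = 0.2) or 0.29 (p = 0.4).

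So at the assumed extremes, testing under the present withdrawal rule would lose more treatment doses (0.45) than it averts in pregnancy (0.31). If a repeat test is required before withdrawal and its error is independent at the same 1%, the 0.45 becomes 0.45 × 0.01 = 0.0045. A result that is false for a lasting reason would repeat, so the reduction is large but not complete.

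**The case against.** The strongest reply is that this is a preference. The documents set no standard that is breached, several safeguards already exist, and treatment stops on mere suspicion, which needs no scheduled assay. That is fair as to error, and the point is offered as an inexpensive improvement only.

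The second reply is that adding tests while leaving the withdrawal rule alone may do net harm to treatment, as step 6 shows. That stands, and it is why the fix includes confirmation before withdrawal. A doses-lost figure and a fetal-exposure figure are not equivalent harms, so the comparison shows only that the trade-off is real.

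Third, the sizing is nearly all assumption. That also stands. The 0.31 is not a strict upper bound: conceptions shortly before dose 1 are left out, which could raise it, while stopping for lung progression, toxicity, withdrawal or death is ignored, which lowers it.

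A reader might infer more than the documents support in four ways:
- *That the Protocol contradicts itself.* It does not: a rule to act on a positive test can coexist with having no scheduled test.
- *That Section 9.1.11 supplies the hazard, where it names* "mutations and a potential for development of hereditary defects". That text stands under secondary malignant neoplasms and concerns the treated patient's own radiation dose. A test after conception does not prevent a heritable mutation. The relevant provisions are those on fetal exposure in 11.3.1.
- *That testing before each dose would prevent fetal exposure.* A woman who conceives between doses may still carry radium from earlier ones (half-life 11.4 days, 9.1.1). The test averts later doses only, and it misses conceptions in roughly the 10 to 21 days before a dose.
- *That no testing is done anywhere.* The consent form is not in the public text, so testing described there cannot be excluded.

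**Conclusion.** The gap is real and verified across the sections: one test before cycle 1, none required before cycles 2 to 6, and hence no scheduled on-treatment test to trigger the positive-test stopping rule. It is worth considering at low priority. The certain part is the age of the single test, 140 to 147 days at dose 6 on schedule. The expected saving, 0 to about 0.31 doses in the trial (0.20 to 0.25 at most with SSE stopping), depends on assumed numbers of women, pregnancy rates and detection times. It is zero if no woman of childbearing potential enrolls. The documents give no fetal dose, so harm per case cannot be sized. Neither the sample size nor the error rates are affected. The fix could shorten the on-treatment window for the first primary endpoint only if a false positive ended treatment, which the confirmation step makes unlikely.

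**What to change.** For women of childbearing potential only:

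1. In Section 6.0, mark the Serum Pregnancy row in the pre-cycle column, within 7 days before each dose, using blood already drawn for the CBC and alkaline phosphatase.
2. In Section 5.1, add *negative pregnancy test within 7 days* to the criteria for cycles 2 to 6, because a calendar entry alone does not control dosing.
3. In Section 12.0 item 7, with a matching line in 11.3.1, state that a positive screening result holds the dose at once and is promptly confirmed by a repeat test before permanent withdrawal. Leave the reporting duties as they are.

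Cost: at most 5 extra routine assays per affected woman (0 to 15 under the assumed 0 to 3 women; 5 × 36 = 180 if every patient qualified), plus the rare repeat. No routine extra visit or blood draw is needed, though a repeat after a positive result may need one. A false positive would cause a short delay. Having the result before the syringe is drawn avoids wasting a dose, since a drawn syringe lasts 4 days (9.1.7). Section 14.3 counts the addition of a safety test among changes that need IRB approval at each center, besides review by BrUOG, Bayer and the investigator, so it is best bundled with the next amendment.
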